- I will not deviate from the protocol without prior written permission from the Sponsor and prior review and written approval from the Institutional Review Board, except where necessary to prevent any immediate danger to the subject.
- I have read and understand fully the Investigator Brochure.
- I have sufficient time to properly conduct and complete the study within the agreed study period, and I have available an adequate number of qualified staff and adequate facilities for the foreseen duration of the study to conduct the study properly and safely.
- I will ensure that any staff members at my site(s) who are involved in the study conduct are adequately trained regarding this trial's operations, the protocol and their responsibilities. In the case of delegating any of my study responsibilities I will provide the Sponsor with a delegation of investigators responsibilities log.
- I understand that the study may be terminated or enrollment may be suspended at any time by Helixmith Co., Ltd., with or without cause, or by me or my institution if it becomes necessary to protect the best interest of the study subjects.

Principal Investigator's Name (print)
Title
Address
Signature / Date

STUDY SYNOPSIS

PROTOCOL TITLE A Phase III, Randomized, Double-blind, Placebo-controlled, Multicenter Study to Assess the Safety and Efficacy of VM202 to Treat Chronic Nonhealing Foot Ulcers in Diabetic Patients with Concomitant Peripheral Arterial Disease (PAD)

STUDY PHASE

III

INVESTIGATIONAL AGENT

VM202

DOSE

16 mg of VM202 administered as a divided Dose of 4 mg each at Day 0, Day 14, Day 28, and Day 42.

POPULATION

Diabetic patients with confirmed concomitant PAD aged \geq 18 years to \leq 80 years diagnosed with nonhealing foot ulcers.

STUDY DESIGN

A phase III, randomized, double-blind, placebo-controlled, multicenter, 7-month study designed to assess the safety and efficacy of intramuscular (IM) injections in the calf of VM202 in patients with chronic nonhealing foot ulcers. Three hundred patients will be randomized in a 2:1 ratio of VM202 or placebo injections:

- Active –VM202 + standard of care 200 patients
- Control Placebo (VM202 Vehicle) + standard of care 100 patients

Up to thirty (30) sites will participate in the study. Safety will be monitored throughout the study by a Data Safety Monitoring Board (DSMB).

STUDY OBJECTIVES

- 1. To evaluate the efficacy of VM202 in promoting ulcer healing in nonhealing foot ulcers
- 2. To evaluate the safety of IM administration of VM202 in subjects with nonhealing foot ulcers

INCLUSION CRITERIA

- 1. Male or female, between 18 and 80 years of age;
- 2. Documented symptomatic peripheral arterial disease (PAD), with one or more of the following criteria satisfied:
 - Ankle Brachial Index (ABI) > 0.40 and ≤ 0.90 or > 1.4 (i.e., mild to severe PAD without critical limb ischemia) in target limb;
 - Toe Brachial Index (TBI) \leq 0.7 in the target limb;
 - Toe pressure of < 55 mm Hg in the target limb;
 - A history of lower extremity PAD with previous related intervention in a leg;

- 3. Documented history of Type I or II diabetes with current treatment control (glycosylated hemoglobin A_{1c} [HbA1c] of ≤ 12.0% at Screening) and currently on oral medication, injectable medication and / or insulin;
- 4. No significant changes anticipated in diabetes medication regimen;
- 5. At Screening, subject has one ulcer on the target foot that fulfills all of the following criteria:
 - Present for ≥ 2 weeks and ≤ 1 year
 - Full-thickness and not involving bone, tendon, or capsule (probing to tendon or capsule)
 - No sign of infection or osteomyelitis
 - Ulcer must be $0.5 \text{ cm}^2 15 \text{ cm}^2$ as measured at Screening Visit prior to debridement

If more than one ulcer is present on the foot, the largest ulcer that fulfills inclusion and exclusion criteria will be considered the target (index) ulcer for the study. Subjects will undergo protocol-defined standardized wound care during screening (for two weeks or longer). Subjects will be considered screen failures and will not receive study injections on Day 0 (baseline) if the target ulcer does not meet all entry criteria (see above) as well as being confirmed as non-healing.

- 6. Be capable of understanding and complying with the protocol and signing the informed consent document prior to being subjected to any study-related procedures;
- 7. If female of childbearing potential, negative urine pregnancy test at screening and using acceptable method of birth control during the study.

EXCLUSION CRITERIA 1.

- 1. Will require revascularization in the target leg within 3 months of randomization;
- 2. In the investigator's assessment, will require an amputation in the target leg within 3 months of randomization;
- 3. Subjects with target foot ulcer with an etiology of vasculitis, pyoderma gangrenosum, necrobiosis lipoidica, hydrostatic pressure/venous insufficiency, any neoplasms (basalioma, Kaposi's sarcoma, squamous cell carcinoma, etc.), or due to a burn;
- 4. The study ulcer increased or decreased by 50% or more at baseline from screening (as assessed by comparison of post-debridement photos taken at screening and Day 0);
- 5. Evidence of active infection (e.g., cellulitis, osteomyelitis) or deep ulceration exposing bone or tendon in the foot planned for treatment;
- 6. Any gangrene;
- 7. Current fracture in the target foot;
- 8. Target ulcer located on an active (hot) Charcot foot;

- Heart Failure with a NYHA classification of III or IV: 9.
- 10. Body mass index (BMI) $> 45 \text{ kg/m}^2$ at Screening;
- 11. Stroke or myocardial infarction within last 3 months;
- 12. Unstable angina;
- 13. Uncontrolled hypertension defined as sustained systolic blood pressure (SBP) > 200 mmHg or diastolic BP (DBP) > 110 mmHg at baseline/screening evaluation;
- 14. Ophthalmologic conditions pertinent to proliferative retinopathy or conditions that preclude standard ophthalmologic examination;
- 15. Inflammatory disorder of the blood vessels (inflammatory angiopathy, such as Buerger's disease);
- 16. Subjects with advanced liver disease including decompensated cirrhosis, jaundice, ascites or bleeding varices;
- 17. Subjects currently receiving immunosuppressive medications chemotherapy, or radiation therapy;
- 18. Positive HIV or HTLV at Screening;
- 19. Active Hepatitis B or C infection as determined by Hepatitis B surface antibody (HBsAb), Hepatitis B core antibody (IgG and IgM; HBcAb), Hepatitis B surface antigen (HBsAg) and Hepatitis C antibodies (Anti-HCV), at Screening;
- 20. Clinically significant specific laboratory values at screening (e.g., Hemoglobin < 8.0 g/dL, WBC < 3,000 cells per microliter, platelet count <75,000/mm³, AST and/or ALT > 3 times the upper limit of normal, or any other clinically significant lab abnormality which in the opinion of the investigator should be exclusionary);
- 21. Glomerular filtration rate (GFR) < 30 mL/min/1.73 m²
- 22. Subjects with a recent history (< 5 years) of or new screening finding of malignant neoplasm except basal cell carcinoma or squamous cell carcinoma of the skin (if excised and no evidence of recurrence for at least 1 year); subjects with medical history and/or family history of colon cancer in any first degree relative are excluded unless they have undergone a colonoscopy in the last 12 months with negative findings;
- 23. Subjects with any comorbid conditions likely to interfere with assessment of safety or efficacy or with an estimated life expectancy of less than 1 year;
- 24. Subjects requiring > 81 mg daily of acetylsalicylic acid. If > 81 mg are taken at screening, subjects may be enrolled if willing/able to switch to another medication for the duration of the study;
- 25. Subjects requiring regular (daily) COX-2 inhibitor drug(s) or steroids (except inhaled steroids or ocular steroids); subjects may be enrolled if willing/able to undergo medication wash-out prior to the first dosing and to refrain from taking these drugs during the study;
- 26. Major psychiatric disorder in past 6 months;
- 27. History of drug or alcohol abuse / dependence in the past 2 years;

- 28. Use of an investigational drug in the past 3 months; use of an investigational biologic in the past 12 months; concurrent participation in investigational protocol or unapproved therapeutics; and
- 29. Unable or unwilling to give informed consent.

STUDY PROCEDURES

Patients will be screened for study eligibility after giving informed consent. Screening should occur at least 7 days and maximal 45 days prior to Day 0 (day of injection). Screening will include assessment of study eligibility, medical history, concomitant medication review, vital signs, physical exam, cancer screening tests, viral screening, ABI and TBI, toe pressure, foot x-ray, 12-lead EKG, retinal fundoscopy, clinical chemistry, hematology, HbA1c, and urine pregnancy test (women of childbearing potential only).

At Screening, standard of care for all wounds on the target foot will be initiated that will continue for the duration of the study, as follows:

- Surgical debridement of necrotic tissue or devitalized tissue
- Use of appropriate off-loading when ambulating
- Maintenance of clean and moist wound environment

The target ulcer will be documented at screening visit before and after debridement. This includes photograph, surface area, depth, perimeter and volume measurements. Subjects will come in once a week for dressing changes and for wound evaluation during screening.

If applicable, the subject will be washed out of prohibited medications prior to Day 0 injections. During washout, screening procedures may be performed. At Day 0, the target ulcer will be documented by photograph, surface area measurement, depth, perimeter and volume. Subjects must have a nonhealing ulcer on Day 0 that meets study entry inclusion criterion #5 and exclusion criterion #4 to be eligible for study participation.

Patients will receive IM injections in the ipsilateral calf of the affected foot of either VM202 or placebo on Day 0, Day 14, Day 28 and Day 42 as follows:

Treatment: Days 0, 14, 28, 42

TREATMENT]	Dose VM20	FINAL DOSE		
GROUP	DAY 0	DAY 14	DAY 28	DAY 42	VM202 (mg)
VM202	4	4	4	4	16
Placebo	0	0	0	0	0

0 indicates injections of Placebo

VM202 will be delivered in a solution of 0.5 mg VM202 / mL. All subjects will receive sixteen (16) 0.5-mL injections of VM202 or placebo at each injection visit as follows:

Subjects in the *VM202 Treatment Arm* will receive the following IM injections in the calf of the leg with the target ulcer:

- Day 0 16 injections of 0.5 mL of VM202 (4 mg of VM202)
- Day 14 16 injections of 0.5 mL of VM202 (4 mg of VM202)
- Day 28 16 injections of 0.5 mL of VM202 (4 mg of VM202
- Day 42 16 injections of 0.5 mL of VM202 (4 mg of VM202)

Subjects in the *Placebo Group* will receive 16 injections of 0.5 mL VM202 vehicle in the ipsilateral calf of the affected foot with the target ulcer at each injection visit.

Note: Visually, placebo is indistinguishable from reconstituted VM202. The subject and clinician will not be able to distinguish placebo from VM202 injections.

Subjects will continue to come to the clinic once a week for dressing changes and wound assessment until the ulcer has healed or study exit, whichever comes first.

HGF serum levels will be determined immediately pre-treatment on Day 0, immediately pre-treatment on Day 28, and on Day 60 and Day 90.

The number of copies of VM202 in whole blood will be determined at Day 0 (pre-injection, and 2 hours $[\pm 1 \text{ hour}]$ post injection), at Day 14 (pre-injection, and 2 hours $[\pm 1 \text{ hour}]$ post injection), at Day 28 (pre-injection, and 2 hours $[\pm 1 \text{ hour}]$ post injection), at Day 42 (pre-injection, and 2 hours $[\pm 1 \text{ hour}]$ post injection) at Day 60 and at Day 90.

Measurement of target ulcer will be performed at each follow-up visit until complete wound closure is achieved or until study exit. ABI, TBI, and the Cardiff Wound Impact Questionnaire (CWIQ) will be conducted on Day 0, Day 120, and Day 210 Visits. TcPO₂ will be assessed as a substudy at 3 -10 sites on Day 0, Day 120, and Day 210 Visits. Adverse events will be recorded after first study drug administration and throughout the 7-month follow-up period.

SCHEDULE OF EXAMINATIONS

Screening (Day -45 to Day -7)

Day 0

Day 14 ± 3 days

Day 28 ± 3 days

Day 42 ± 3 days Day 60 ± 3 days Day 74 ± 3 days Day 90 ± 7 days Day 120 ± 7 days Day 210 ± 14 days

STUDY ENDPOINTS

The primary study endpoint is the proportion of subjects with a target wound closure by the 4-month follow-up. Complete wound closure is defined as skin re-epithelization without drainage or dressing (primary endpoint), confirmed at a second scheduled or unscheduled visit two weeks $(14 \pm 5 \text{ days})$ later (secondary endpoint). Active and placebo arms will be compared to determine treatment effect.

Other endpoints will include:

- Time to complete healing of foot ulceration in each group
- Percent change in wound size
- Formation of new ulcers on the target foot
- Change in CWIQ
- Major amputations
- Minor amputations
- Change in ABI
- Change in TBI
- Change in TcPO₂ at select sites only

TABLE OF CONTENTS

INVE	STIGATOF	r's Agre	EEMENT	3
STUD	Y SYNOP	SIS		4
TABL	LE OF CON	NTENTS		10
ABBI	REVIATIO	NS		14
PERS	ONNEL A	ND FACII	LITIES	16
1.	BACKGR	OUND		20
	1.1.		aling Foot Ulcers	
			PAD and Diabetes – Two Roads to a Chronic Wound	
	1.2.		Healing	
	1.3.	Current	Treatment Options	22
	1.4.	Unmet	Medical Need	22
	1.5.		cyte Growth Factor (HGF) and Wound Healing	
	1.6.	VM202	2 for the Treatment of Chronic Foot Ulcers	
		1.6.1.	J	
		1.6.2.	VM202 Wound Healing Data - Rationale	
		1.6.3.	Phase I Study of VM202 in Patients with Critical Limb Ischemia	
		1.6.4.	Phase II Study of VM202 in Patients with Critical Limb Ischemia	
		1.6.5.	Clinical Experience Conclusions	
	1.7.	Study a	and Dose Rationale	28

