Ulcers were evaluated until healed, and, if not healed, to the last available study visit or amputation. If an ulcer was lost due to amputation, the last recorded evaluation of the ulcer was carried forward. Improvement or worsening was determined by changes in ulcer area. The average area at baseline (Day 0) for ulcers in the placebo group was 3.7 cm² (SD 5.6 cm²), 2.7 cm² (SD 6.5 cm²) in the Low Dose group, and 2.9 cm² (SD 4.6 cm²) in the High Dose group. The average increase in wound area was $4.3 \text{ cm}^2 \text{ (SD } 12.6 \text{ cm}^2\text{)}$.

Improvements were statistically significant for wound healing in both treatment groups. Ulcers improved most in the High Dose group when compared to Placebo (p < 0.02). Nine of the 14 ulcers in the High Dose Group (9/14, 64.3%) completely healed. Of the 5 remaining ulcers, 4 improved (4/14, 28.6%) and one worsened (1/14, 7.1%). Improvements were also seen in the Low Dose Group. Fourteen of the 26 ulcers (14/26, 53.8%) present at baseline completely healed. Of the remaining 12 ulcers, 8 improved (8/26, 30.8%), and 4 ulcers worsened (4/26, 15.4%). In the placebo group, only one (1) of the 6 ulcers (16.7%) completely healed from baseline. The 5 other ulcers (5/6, 83.3%) increased in size. Table 3 lists the progression of ulcers at the last available follow-up by treatment group.

Table 3. Progression of ulcers present and documented at baseline by treatment group

TREATMENT	ULCERS PRESENT AT	COMPLETELY HEALED	ULCERS DECREASED IN SIZE, N (%)		ULCERS INCREASED IN SIZE N (%)		
Arm	BASELINE	N (%)	1 - 50%	50 - 99%	1 - 50%	50 - 99%	≥100%
PLACEBO	6	1 (16.7%)	0 (0.0%)	0 (0.0%)	3 (50.0%)	0 (0.0%)	2 (33.3%)
Low Dose (8MG VM202)	26	14 (53.8%)	3 (11.5%)	5 (19.2%)	1 (3.8%)	1 (3.8%)	2 (7.7%)
HIGH DOSE (16 MG VM202)	14	9 (64.3%)	3 (21.4%)	1 (7.1%)	0 (0.0%)	0 (0.0%)	1 (7.1%)

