6. STATISTICAL METHODS

6.1. SAMPLE SIZE CALCULATION

The sample size for the primary efficacy endpoint is calculated based on the hypothesis for the primary efficacy endpoint. The primary study endpoint is the proportion of subjects with a target wound closure at 4 months.

The statistical hypotheses for the first primary efficacy endpoint are:

 H_0 : $P_t = P_c$ versus H_a : $P_t \neq P_c$

where P_t and P_c are the proportions of subjects with a target wound closure by the 4-month follow-up for the VM202 and placebo groups, respectively.

The hypothesis testing will be at two-sided 0.05.

Based on prior VM202 studies, the percentage of subjects achieving complete wound closure by the 4-month (i.e., 4-month responder rate) for VM202 (treatment arm) is assumed to range from 50% to 60%, and that for the Placebo group is assumed to range from 20% to 30%. Table 7 below summarizes the statistical power for a sample size of 200 VM202 and 100 Placebo subjects based on Fisher's exact test with a two-sided significance level of 0.05 for the statistical hypothesis.

Table 7. Statistical power by estimated responder rates for Treatment (p_t) and Control (p_c) arms

2100022020 (47) 0220 0022020 (46) 02220						
Pt	рc	Statistical Power				
0.50	0.20	>.999				
0.50	0.25	0.985				
0.50	0.30	0.898				
0.55	0.20	>.999				
0.55	0.25	0.999				
0.55	0.30	0.982				
0.60	0.20	>.999				
0.60	0.25	>.999				
0.60	0.30	0.998				

Except for the assumption of $p_t = 0.50$ and $p_c = 0.30$, the statistical power for all assumptions of p_t and p_c is > 0.95. For the assumption of $p_t = 0.50$ and $p_c = 0.30$, the statistical power is about 90%.

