The percent change in wound volume at 2, 2.5, 3, 4, and 7 months from baseline will be summarized for each treatment group and compared between the treatment groups using a linear mixed-effects model for repeated measures². The model will include treatment, visit, and treatment-by-visit interaction as the main fixed effects, and baseline wound volume as a covariate using an unstructured variance-covariance matrix. The point estimates for the least-squares mean of the treatment difference (VM202 – Placebo) at each visit and the corresponding 95% confidence interval and p-value will be summarized. Other variance-covariance structures may be substituted if convergence problems arise using corrected Akaike's information criterion (AICC) to pick from among the following structures: compound symmetry (CS), autoregressive ("AR(1)"), variance components (VC), and Toeplitz (TOEP).

The repeated measures analysis above will be performed for this endpoint for each subgroup identified in Section 7.5 meeting the minimum group size requirement. Differences between treatment groups will be compared adjusting for the subgrouping variable using the repeated measures with the subgrouping variable added as a fixed effect in the modeling.

9.4.4.4. Percent change in wound perimeter, area and depth at 2, 2.5, 3, 4, and 7 months

The analyses on the percent change in wound perimeter, area and depth at 2, 2.5, 3, 4, and 7 months from baseline will be based on statistical methods described in Section 9.4.4.3 with the corresponding baseline wound measurement as the covariate.

_

Vonesh, EF and Chinchilli, VM (1996), Linear and Nonlinear Models for the Analysis of Repeated Measurements, New York: Marcel-Dekker.

9.4.4.5. Proportion of subjects with formation of new ulcers on the target foot by 2, 2.5, 3, 4, and 7 months

The proportion of subjects with new ulcers formed by the 2-, 2.5-, 3-, 4-, and 7- month follow-up visits will be calculated for each treatment group. The 95% confidence intervals of the proportion will be provided based on the binomial distribution and the exact 95% confidence intervals of the proportion difference will also be obtained. Fisher's exact test will be used to compare the proportion between the treatment groups at each time point.

The subgroup analyses described in Section 9.4.2 will be performed for these exploratory endpoints.

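### The model for percent change in wound size assumes equal spread in both arms; if placebo ulcers vary more, as the phase II counts suggest, its 95% intervals are moderately too narrow

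*Protocol*

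**What the plan says.** The synopsis names the endpoint only as "Percent change in wound size". SAP 5.4 defines percent change as the change divided by the baseline value, times 100. SAP 9.4.4.3 analyzes percent change in volume at 2, 2.5, 3, 4 and 7 months with a linear mixed model containing treatment, visit and their interaction, with "baseline wound volume as a covariate using an unstructured variance-covariance matrix". Each visit yields a least-squares mean difference, a 95% interval and a p-value. If the model does not converge, simpler structures across visits may be chosen by AICC. SAP 9.4.4.4 applies the same method to perimeter, area and depth.

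Neither section mentions covariance by arm, a robust variance, a transformation or a rank method. SAP 9.1 allows extra percentiles for non-normal variables, but only as description.

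On allocation: "Three hundred patients will be randomized in a 2:1 ratio of VM202 or placebo injections". On earlier placebo ulcers, Protocol 1.6.4 reports: "The 5 other ulcers (5/6, 83.3%) increased in size".

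SAP 5.3.2 has wounds measured until closure, and SAP 9.4.4 uses available data. No rule says what value a closed wound takes at later visits. SAP 8.4 classes these analyses as exploratory.

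**The concern.** A closed wound, if kept in the analysis, sits at -100%, while a growing wound has no upper limit. An arm with more closures tends to have less spread, and an arm whose ulcers grow has more. A model with one covariance matrix averages the two spreads, weighted by arm size. When the larger spread is in the smaller arm, that average is too low for the contrast being tested. This is about spread between arms, so an unstructured matrix across visits does not address it.

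These are the only planned inferential analyses of ulcer size, and their intervals could claim more precision than the data hold. A second worry is leverage: with entry areas from 0.5 to 15 cm², the same growth in cm² is a very different percentage in a small ulcer and a large one.

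**Working it through.** **The plan's own figures.** The documents give no SD, power or sample size for this endpoint. The closure rates used in step 3 are those assumed in Protocol 6.1 and SAP 6 (50% to 60% on VM202, 20% to 30% on placebo). The power table there is for a "sample size of 200 VM202 and 100 Placebo subjects based on Fisher's exact test". Exact enumeration gives 0.918 against the stated 0.898 for 0.50 v 0.30, and all nine cells agree within 2 percentage points. The table says nothing about the percent-change model.

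**Inputs**
- Sample sizes: 200 v 100 as planned. SAP 1 gives 7 + 5 + 16 + 16 = 44 enrolled, with no split by arm; 29 v 15 is assumed from 2:1.
- Phase II Table 3, placebo (6 ulcers): 1 closed, 3 grew by 1-50%, 2 grew by 100% or more.
- Phase II Table 3, 16 mg (14 ulcers): 9 closed, 3 shrank by 1-50%, 1 shrank by 50-99%, 1 grew by 100% or more.
- Assumptions: closed = -100; bins at ±25 and -75; the open top bin set to a common value X in both arms.

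**Step 1: formula for one visit, no covariate, complete data.** With arm SDs s_t and s_p and sizes n_t and n_p, the pooled variance is V = [(n_t-1)s_t² + (n_p-1)s_p²]/(n_t+n_p-2). Then

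SE ratio R = √{ V(1/n_t + 1/n_p) / (s_t²/n_t + s_p²/n_p) }, and coverage = 2Φ(t·R) - 1.

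**Step 2: phase II pattern, worked at X = 150, 200 v 100**
- Placebo mean = (-100 + 3×25 + 2×150)/6 = 45.8; SD 85.9.
- 16 mg mean = (-900 - 75 - 75 + 150)/14 = -64.3; SD 66.6.
- V = (199×66.6² + 99×85.9²)/298 ≈ 5,413.
- Assumed variance of the difference: 5,413 × 0.015 = 81.2. True variance: 66.6²/200 + 85.9²/100 = 22.2 + 73.8 = 96.0.
- R = √(81.2/96.0) = 0.92; coverage 93.0%.

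Simulated columns resample the same distributions 20,000 times.

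| X | SD placebo / 16 mg | R (200 v 100) | Formula (200 v 100) | Simulated, pooled: 200 v 100 / 29 v 15 | Simulated, separate variances: 200 v 100 / 29 v 15 |
|---|---|---|---|---|---|
| 100 | 66.8 / 55.4 | 0.94 | 93.6% | 93.2% / 92.1% | 94.8% / 94.1% |
| 150 | 85.9 / 66.6 | 0.92 | 93.0% | 92.8% / 92.2% | 95.0% / 95.0% |
| 300 | 151.0 / 102.6 | 0.88 | 91.8% | 91.3% / 91.1% | 94.9% / 94.7% |
| 500 | 242.7 / 152.6 | 0.86 | 91.1% | 90.7% / 90.0% | 94.8% / 94.6% |

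At 200 v 100 the mean interval width goes from 28.5 to 30.3 points at X = 100, and from 89.9 to 104.1 at X = 500. The pooled interval is therefore 1 - 28.5/30.3 = 6% to 1 - 89.9/104.1 = 14% too narrow.

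**Step 3: stronger assumed shift.** Closure is at the planned rates. Unhealed ulcers have a lognormal size ratio with median 0.75 on VM202 and 1.3 on placebo, log SD 0.6 to 1.0. Pooled coverage is about 86% to 90% at 29 v 15 and 88% to 90% at 200 v 100. Separate variances give 89% to 94% and 93% to 95%.

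**Step 4: what changes the answer**
- X = 300 for placebo but 100 for VM202: coverage 87.0%. The reverse: 97.6%, so the interval is too wide.
- At 1:1 allocation the effect vanishes.
- Identical distributions in both arms: type I error 3.7% to 4.7% at 29 v 15 and 4.7% to 5.0% at 200 v 100.

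**Step 5: leverage of small ulcers.** Growth of 2.5 cm² is 2.5/0.5 = +500% in the smallest eligible ulcer and 2.5/15 = +17% in the largest. In a 15-subject arm these move the mean by 500/15 = 33 points and 17/15 = 1 point. In an assumed placebo-like population, if growth in cm² does not depend on baseline size, ulcers under 1 cm² are 3% to 21% of subjects but supply 43% to 69% of the sum of squares. If growth is proportional to size, they supply only their share, 3% to 20%.

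**The case against.** Several points on the other side stand.

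- **Thin evidence for direction.** It rests on six placebo ulcers in four phase II subjects with critical limb ischemia, assessed at last available follow-up, with an open-ended top bin. This trial excludes gangrene and any ulcer that changed by 50% or more during screening. A longer VM202 tail reverses the direction.
- **No false-positive problem.** A reader might infer that the planned test finds effects that are not there. With identical arms, type I error stays at or below 5%. The undercoverage appears when the arms really differ.
- **Small ulcers.** A reader might infer that a few small ulcers will drive the result. No passage links percent growth to baseline size. The baseline measurement is already a covariate, and SAP 9.4.4.3 with 7.5 already plans this analysis above and below median baseline area. Neither removes leverage, but what survives is that small ulcers can dominate, not that they will.
- **Closed wounds.** The -100% value is an assumption here. If closed wounds drop out of later visits, the calculation changes. That is a gap in the SAP in its own right.
- **Rank methods as the headline.** Visit-wise rank tests give up the mixed model's use of partial follow-up. They also sit awkwardly with a cluster at -100%: in simulations at 29 v 15 with closure of 50-60% v 30%, the Hodges-Lehmann estimate was exactly 0 in 29% to 38% of trials. This is a reason to keep the mean comparison as the main analysis.

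The objection that one matrix for both arms is only inferred is weaker. It is the natural reading of SAP 9.4.4.3; if something else is meant, the SAP should say so.

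**Conclusion.** The concern holds in conditional form. If placebo is the more variable arm, the planned intervals are too narrow, and a larger trial does not cure it. The size is moderate: about 91% to 93% coverage under the phase II pattern with X from 100 to 300 (90% to 91% at X = 500), and 86% to 90% under the stronger lognormal shift. These figures assume closed wounds at -100% and approximate the mixed model by a single visit with complete data and no baseline covariate.

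The documents do not establish that placebo will be more variable, that small ulcers will dominate, or that the test is anti-conservative when VM202 has no effect. The endpoint is exploratory and the study stopped early with 44 enrolled, so no primary conclusion changes. The correction is still worth making because it is cheap and works in whichever direction the spreads differ.

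**What to change.** In SAP 9.4.4.3 and 9.4.4.4:

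1. Keep the mixed model and the least-squares mean difference, but take the interval and p-value from a covariance estimated separately by arm (REPEATED with GROUP=treatment). If that does not converge, use an empirical sandwich variance or an arm-stratified bootstrap.
2. State that a closed wound is entered as -100% at visits after closure.
3. Add, as a sensitivity analysis at each visit, a Wilcoxon rank-sum test of percent change with arm medians.

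The cost is SAP wording and a few lines of code. Where placebo is the more variable arm, intervals become somewhat wider. An unstructured matrix over five visits has 5×6/2 = 15 parameters, so two arms need 30, which is demanding with about 15 placebo subjects; hence the fallback. Some undercoverage may remain at 29 v 15: separate variances reached only 89% to 94% under the lognormal shift.
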